9.2.1.2. Dose Limiting Toxicity

DLT will be assessed during the first 3 weeks of treatment with bemcentinib (Cycle 1), according to the National Cancer Institute (NCI) Common Terminology Criteria for Adverse Events (CTCAE) [NCI CTCAE] version 4 considered unrelated to leukemia progression or intercurrent illness, and defined as any of the following:

- CTCAE Grade 3 or 4 nausea, vomiting, or diarrhea that persists despite maximum prophylactic and supportive care.
- Any other CTCAE Grade 3 or 4 non-hematological toxicity that is considered to be clinically significant and causally related to bemcentinib, excluding isolated changes

in laboratory results if no clinical significance or no clinical sequelae and adequately improve within 7 days.

- Prolonged neutropenia with ANC <500 and platelet count <75000 after Day 42 from the start of treatment in the absence of residual leukemia.
- Treatment discontinuation, inability to administer one or more bemcentinib loading dose, or inability to administer three bemcentinib maintenance doses as a result of bemcentinib-related toxicity.
- Any ventricular arrhythmia.

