12.2. Dose Modification

12.2.1. Bemcentinib

If a patient experiences drug-related toxicity which requires treatment with bemcentinib to be interrupted, a delay of up to 14 days is permitted to allow for resolution of toxicity. Toxicities must have resolved to Grade ≤ 1 or to baseline for treatment to recommence. For Grade 1 or Grade 2 (tolerable) toxicity, the patient may resume dosing at the same dose level. For \geq Grade 2 (intolerable) toxicity, the patient may resume dosing at a dose level defined by the grade of the toxicity and the number of occurrence(s) of prior toxicity as outlined in Table 7. A maximum of two dose reductions are permitted.

Table 7: Dose Modification of Bemcentinib Daily Dose for Toxicity

Grade (CTCAE)	Recommended Dose Modification
Grade 1 and Grade 2 (tolerable)	
Any occurrence	Maintain dose if toxicity is tolerated by the patient
Grade 2 (intolerable)	
1 st or 2 nd occurrence of same adverse event	Interrupt treatment until toxicity returns to baseline, Grade 1 or tolerable Grade 2 Resume dosing at same dose
3 rd occurrence of same adverse event	Interrupt treatment until toxicity returns to baseline, Grade 1 or tolerable Grade 2 Dose reduce by 100 mg
4th occurrence of same adverse event	Discontinue permanently
Grade 3	
1 st occurrence	Interrupt treatment until toxicity returns to baseline, Grade 1 or tolerable Grade 2 Dose reduce by 100 mg or Discontinue permanently if dose has already been reduced
2 nd occurrence of same adverse event at G3	Discontinue permanently
Grade 4	
1 st occurrence	Discontinue permanently
Notes:	

• Treatment interruption for bemcentinib-related toxicity should be limited to 14 days• Dose reduction below 100 mg daily is not possible (a single capsule contains 100 mg bemcentinib)• Patients being considered for dose reduction or permanent discontinuation of bemcentinib, should be discussed with the Medical Monitor	

If after a 14-day delay, toxicity has not resolved to Grade ≤ 1 or to baseline the patient should be withdrawn from the study.

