12.5. Discontinuation of Treatment and Withdrawal of Patients

Patients may withdraw informed consent and discontinue from the study at any time, or for any reason, without prejudice to their future treatment. In addition, a patient must be discontinued from the study if any of the following criteria are met:

- Significant patient non-compliance with the protocol, as agreed by the investigator and the sponsor
- Patient lost to follow-up
- Termination of the study by the sponsor
- Patient experiences an unacceptable toxicity that precludes them from continuing in the study e.g. patient experiences a ventricular arrhythmia (see Section 12.2.1), as agreed by the investigator and the sponsor
- Lack of adequate recovery from a first cycle DLT, see Section 9.2.1.2
- Failure of toxicity to adequately resolve, as outlined in Table 7
- Female patient becomes pregnant

- Patient experiences PD (unless in the opinion of the investigator, they continue to derive clinical benefit and are permitted to continue on study after discussion and agreement between investigator, the patient and Sponsor. All decisions will be documented in writing).

Note: Clinical benefit in this context is defined as meeting one or several of the following criteria: evidence of disease stabilization after documented initial progression (patient is stably worse), tolerance of drug(s), absence of rapid progression based on peripheral or bone marrow blasts and clinical hematology and clinical chemistry parameters, maintenance of good performance status (PS of 2 or less and not deteriorating], absence of worsening clinical symptoms (i.e., no symptomatic deterioration) and/or improvements in patient's quality of life). This will not affect the time point of disease progression from the perspective of trial analysis.

- Patient and/or investigator decide that it is in the patient's best interest to withdraw from study treatment or the patient withdraws consent

AEs resulting in discontinuation will be followed as outlined in Section 9.3.4.

Patients who discontinue during the DLT assessment period (Part A), for any reason other than a DLT, will be replaced. All other patients who discontinue study treatment will not be replaced.

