## 4.6 Withdrawn Subjects

Patients may withdraw informed consent and discontinue from the study at any time, or for any reason, without prejudice to their future treatment. In addition, a patient must be discontinued from the study if any of the following criteria are met:

- Patient non-compliance with the protocol, as agreed by the investigator and the sponsor
- Patient lost to follow-up
- Termination of the study by the sponsor
- Patient experiences an unacceptable toxicity that precludes them from continuing in the study e.g. patient experiences a ventricular arrhythmia (see study protocol Section 12.2), as agreed by the investigator and the sponsor

- Lack of adequate recovery from a DLT, see Section 9.2.1.2 in study protocol
- Failure of toxicity to adequately resolve, as outlined in Section 12.2 in study protocol
- Female patient becomes pregnant
- Patient experiences clinical disease progression
- Patient and/or investigator decision

AEs resulting in discontinuation will be followed as outlined in study protocol Section 9.3.4.

Patients who discontinue during the DLT assessment period (Part A), for any reason other than a DLT, will be replaced. All other patients who discontinue study treatment will not be replaced.

If a patient discontinues treatment prior to study completion, and for reasons other than progression or non-tolerability, every effort should be made to conduct the Final Study Visit assessments as outlined in Section 11.5 of the protocol. The reason for the patient's withdrawal from the study must be recorded in the eCRF.

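### Protocol 12.2.1 sets two different thresholds for restarting bemcentinib, and for withdrawal at 14 days, after non-QTc toxicity

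*Protocol*

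**What the plan says.** Protocol Section 12.2.1 allows bemcentinib to be held for up to 14 days for drug-related toxicity. The opening text then sets a mandatory condition: "Toxicities must have resolved to Grade" ≤1 "or to baseline for treatment to recommence". The sentence after Table 7 uses the same threshold for the opposite outcome. If, after the 14-day delay, the toxicity has not reached Grade ≤1 "or to baseline the patient should be withdrawn from the study".

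Table 7 lies between these two sentences. It has seven action rows: one keeps the dose, three interrupt it and three stop it for good. All three interruption rows (intolerable Grade 2, first or second occurrence; intolerable Grade 2, third occurrence; Grade 3, first occurrence) carry the same instruction: "Interrupt treatment until toxicity returns to baseline, Grade 1 or tolerable Grade 2".

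Two other places point back to these rules. Protocol Section 12.5 lists among the reasons for which a patient must be discontinued "Failure of toxicity to adequately resolve, as outlined in Table 7". SAP Section 4.6 has "Failure of toxicity to adequately resolve, as outlined in Section 12.2 in study protocol". QTc prolongation is handled separately in Table 8.

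**The concern.** A site holding a patient who has improved to tolerable Grade 2 finds one instruction that permits dosing and another that forbids it, both within Section 12.2.1. If the toxicity is still at that grade at day 14, the choice is between continuing on drug and leaving the study.

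Safety and tolerability is the primary objective of Part B. SAP Section 5.6 tabulates the number and duration of dose interruptions, and SAP Section 5.3 reports reasons for discontinuation. If sites follow different sentences, these summaries mix two dosing rules. For the patient, the stake is either re-exposure before the toxicity has resolved or loss of treatment in a setting that Section 12.4 describes as one of high unmet need.

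**Working it through.** The plan gives no figure to reproduce, so the check sets the rules side by side.

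| Place in protocol 12.2.1 | Restart allowed at | Then |
|---|---|---|
| Opening text | Grade ≤1 or baseline (mandatory) | dose level per Table 7 |
| Table 7, intolerable Grade 2, 1st or 2nd | baseline, Grade 1 or tolerable Grade 2 | same dose |
| Table 7, intolerable Grade 2, 3rd | as above | reduce by 100 mg |
| Table 7, Grade 3, 1st | as above | reduce by 100 mg, or stop if already reduced |
| Sentence after Table 7 | Grade ≤1 or baseline | withdraw if not met after 14 days |

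**When the rules differ.** Let g0 be the baseline grade and g the current grade. The text allows restart if g ≤ 1 or g ≤ g0. Table 7 also allows it if g = 2 and tolerable. They therefore disagree only when g = 2 (tolerable) and g0 is 0 or 1. If g0 is already 2, both allow restart.

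**Effect within the 14 days.** Let a be the day of interruption on which tolerable Grade 2 is reached and b the day on which Grade ≤1 or baseline is reached, in whole days with 1 ≤ a ≤ b ≤ 14. The interruption may end at day a under Table 7 and at day b under the text. The gap is b − a, from 0 to 14 − 1 = 13 days.

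**Effect at day 14.** If a ≤ 14 but Grade ≤1 or baseline has not been reached by then, Table 7 permits dosing and the closing sentence calls for withdrawal.

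**Does anything else settle it?**
- Section 12.5 cites Table 7, which carries the looser rule. SAP Section 4.6 cites the whole of Section 12.2, which in this protocol holds both.
- The sentence "For Grade 1 or Grade 2 (tolerable) toxicity, the patient may resume dosing at the same dose level" concerns the dose on resumption. Read as permission to restart at residual Grade 2, it would contradict the mandatory sentence before it. It would also imply same-dose restart where two Table 7 rows call for a 100 mg reduction.
- A Table 7 note sends patients considered for dose reduction or permanent discontinuation to the Medical Monitor. That reaches the third-occurrence Grade 2 row, the Grade 3 row and a day-14 discontinuation. It does not reach same-dose restart after a first or second intolerable Grade 2 event.

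**Who is within reach.** Protocol Section 16.8 reports Parts A and B3 complete, B2 closed to enrolment with patients ongoing, and B1, B4 and B5 enrolling as of 17 March 2020. The planned ceiling in the parts then running is 14 (B1) + 14 (B2) + 14 (B4) + 20 (B5) = 62 evaluable patients. Only those with an interruption that passes through tolerable Grade 2 are affected, and the documents do not say how many that would be.

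**The case against.** The best defence is that a hierarchy is implied. The text says must, and it sends the reader to Table 7 only for the dose level. The table's column is headed as a recommendation, and the closing sentence repeats the strict threshold. A site that waits for Grade ≤1 or baseline breaks neither restart rule. This has force: a compliant path exists, and the strict reading is probably the one intended. It does not close the matter. Section 12.5 makes failure to resolve under Table 7 a mandatory reason for discontinuation, so the table is more than advisory, and the looser wording appears in every interruption row.

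It is also fair that the interruption tables are descriptive and will report what happened under either rule. Further, the SAP names US protocol Version 9.0 and three other country protocols, whereas the text reviewed is US v10.0; whether those documents carry the same conflict cannot be checked here.

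A reader might infer more than the documents support:
- *That the conflict changes dose-limiting toxicity calls and the maximum tolerated dose.* Part A does count "inability to administer three bemcentinib maintenance doses as a result of bemcentinib-related toxicity" as dose limiting, so a longer wait could matter there in principle. But Part A is complete, so no amendment can alter it. A clinically significant, bemcentinib-related Grade 3 non-hematological event is dose limiting whatever the restart date.
- *That it triggers repeat loading doses.* That recommendation is in footnote c of Table 4, which covers Part A; footnote c of Tables 5 and 6 does not contain it.
- *That Table 7 strands patients on 100 mg who have never been reduced.* Part B is stated at 400/200 mg, so this hardly arises in the ongoing parts.

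**Conclusion.** The concern holds as an internal inconsistency in a safety instruction. For ongoing Part B patients with a baseline grade below 2, the restart date, and withdrawal or continuation at day 14, depend on which sentence a site follows. The gap is at most 13 days per interruption, plus a stay-or-leave decision at day 14. The one path with no Medical Monitor check under the Table 7 note is same-dose restart after a first or second intolerable Grade 2 event.

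This should be corrected, but its reach is limited. The sample size and the objective response test are unaffected, and the number of patients involved is unknown. The conclusion rests on the US v10.0 text and on the study status given in Section 16.8. For any part that has since finished, only the reporting element remains.

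**What to change.** Use one threshold in the opening text, the three Table 7 interruption rows and the closing sentence.

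**Default:** delete the tolerable Grade 2 alternative from the three rows. This agrees with the mandatory text and with Table 8, where restart after an interruption requires Grade ≤1. (One Table 8 branch allows a second 100 mg reduction without resolution. From 200 mg, the first reduction leaves 100 mg, the lowest available dose, so that branch ends in discontinuation.) The price is somewhat longer interruptions and possibly more withdrawals at day 14. It also leaves a patient who was never interrupted free to continue at tolerable Grade 2 under the first row of Table 7, while an interrupted patient at that grade must wait or leave.

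**Alternative:** if the sponsor intends the looser rule, which fits that first row, add tolerable Grade 2 to both text sentences instead.

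In either case, state in the study report which rule was applied in the completed parts. The cost is a wording amendment to protocol 12.2.1 and one sentence in the report. No new procedures are needed, and no SAP change, because SAP 4.6 refers to Section 12.2 as a whole. If the other country protocols carry the same wording, they need the same edit.

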12.3. Concomitant Medication and Procedures

All prescription, non-prescription, or over-the-counter medications including herbal remedies given to, or taken by, the patient at entry and during the study must be clearly documented in the eCRF.

The patients must be instructed that no additional medication will be allowed without the prior consent of the investigator. Any medication considered necessary for the patient's safety and well-being may be given at the discretion of the investigator. Hematopoietic growth factors may be administered for the treatment of AEs such as neutropenic infections but should not be used to maintain the dose intensity of bemcentinib in Part A. Patients who have evidence of treatment benefit after \geq 1 cycle of treatment in Part B may receive hematopoietic growth factors to maintain bemcentinib dosing.

Concurrent treatment with any agent known to cause QT prolongation and have a risk for Torsades de Pointes is an exclusion criterion for the study. A comprehensive list of these prohibited medications is provided in Appendix 3. Patients being treated with antacid histamine receptor 2 inhibitors or proton pump inhibitors within 3 days of administration of bemcentinib will be excluded. The Investigator may initiate treatment with these medications during the study, providing they are taken in the evening.

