Formulation 2 includes additional excipients resulting in an improved solubility profile when compared to Formulation 1. Repeated doses of Formulation 2 have already been administered to NSCLC patients in the fasting state in Study BGBC004, where drug absorption was increased and less variable when compared to data from patients receiving Formulation 1. pH studies suggest that bemcentinib exhibits increased solubility in an acid environment, thus patients should receive Formulation 2 in the fasted state upon waking and should not be receiving baseline gastric protectants including Proton Pump Inhibitors, Histamine Receptor two antagonists or antacids when starting therapy with bemcentinib. They may receive treatment with these agents in the evening if required for symptoms; but only when established on bemcentinib therapy (i.e. following at least one week of treatment with bemcentinib).

The increased absorption of bemcentinib seen with Formulation 2 in Study BGBC004 was well tolerated following a loading dose of 600 mg on Days 1 and 2, followed by a daily dose of 200 mg, but because of the increased bioavailability of this preparation, a starting loading dose of 200 mg administered on Days 1, 2 and 3 followed by a daily maintenance dose of 100 mg will be introduced for Formulation 2 in Study BGBC003.

This dose may be escalated as agreed by the SMC to a maximum daily loading dose of 400 mg on Days 1, 2 and 3 followed by a maximum daily maintenance dose of 200 mg.

Further details of the physicochemical properties of Formulation 1 and Formulation 2 and ongoing clinical studies with Formulation 2 can be found in the current version of the bemcentinib IB and the investigational medicinal product dossier (IMPD).

8. Study Objectives and Endpoints

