aminotransferase (AST) ≥ 2.5 times the ULN (or ≥ 5 times the ULN for AST or ALT in the presence of liver involvement by leukemia)

9. Inability to tolerate oral medication
10. Existing gastrointestinal disease affecting drug absorption such as celiac disease or Crohn's disease
11. Known lactose intolerance
12. Requires vitamin K antagonists. Note: Patients receiving low doses prescribed to maintain the patency of venous access devices may be included
13. Treatment with any of the following; histamine receptor 2 inhibitors, proton pump inhibitors or antacids within 3 days or 5 half-lives of administration of bemcentinib, whichever is longer
14. Treatment with any medication which is predominantly metabolized by CYP3A4 and has a narrow therapeutic index. Please see Appendix 4 for details of CYP3A4 substrates.
15. Previous bowel resection that would interfere with drug absorption
16. Evidence of ongoing gastrointestinal graft versus host disease
17. Hematopoietic stem cell transplantation within 6 months
18. Impaired renal function as demonstrated by a creatinine clearance of <30 mL/min determined by Cockcroft-Gault formula
19. Radiotherapy or chemotherapy within the 14 days prior to the first dose of bemcentinib being administered (other than hydroxyurea)
20. Receiving an investigational anti-cancer treatment concurrently or within 14 days or five half-lives (whichever is shorter) of either the parent drug or any known active metabolite prior to the start of bemcentinib
21. Unresolved CTCAE \geq Grade 2 toxicity (other than stable toxicity) from previous anti-cancer therapy excluding alopecia

22. Any evidence of severe or uncontrolled systemic conditions (e.g., severe hepatic impairment) or current unstable or uncompensated respiratory or cardiac conditions which makes it undesirable for the patient to participate in the study or which could jeopardize compliance with the protocol
23. Known active, uncontrolled central nervous system (CNS) disease including CNS leukemia
24. Active infection with human immunodeficiency virus (HIV), hepatitis B or C viruses – screening for viral infections is **not** required for entry to this study
25. Major surgery within 28 days prior to the start of bemcentinib – excluding skin biopsies and procedures for insertion of central venous access devices
26. Hypersensitivity to cytarabine, decitabine or any of their excipients
27. Prior exposure to Astellas ASP2215 (FLT3/AXL inhibitor Gilteritinib)

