### 4.4 Concomitant Medication and Procedures

All prescription, non-prescription, or over-the-counter medications including herbal remedies given to, or taken by, the patient at entry and during the study must be clearly documented in the eCRF.

The patients must be instructed that no additional medication will be allowed without the prior consent of the investigator. Any medication considered necessary for the patient's safety and well-being may be given at the discretion of the investigator. Hematopoietic growth factors may be administered for the treatment of AEs such as neutropenic infections but should not be used to maintain the dose intensity of bemcentinib in Part A. Patients who have evidence of treatment benefit after  $>1$  cycle of treatment in Part B may receive hematopoietic growth factors to maintain bemcentinib dosing.

Concurrent treatment with any agent known to cause QT prolongation and have a risk for Torsades de pointes is an exclusion criterion for the study. A comprehensive list of these prohibited medications is provided in the study protocol Appendix 3.

Treatment with any medication which is predominantly metabolized by CYP3A4 and has a narrow therapeutic index is also excluded (see Appendix 4 in study protocol for details of CYP3A4 substrates). Patients being treated with antacid histamine receptor 2 inhibitors or proton pump inhibitors within 3 days of administration of bemcentinib will be excluded. The Investigator may initiate rescue treatment with these medications in the evening for symptomatic relief following one week's treatment with bemcentinib.

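### Protocol 12.3 lets acid-reducing drugs start during the loading days, while Protocol 7.2.3.1 and SAP 4.4 require one week of bemcentinib first; washout and drug classes also differ between sections

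*Protocol*

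**What the plan says.** **When the drugs may be started.**
- Protocol 12.3: the investigator may start them during the study, "providing they are taken in the evening". Evening use is the only condition.
- Protocol 7.2.3.1: evening use if symptoms require it, "but only when established on bemcentinib therapy (i.e. following at least one week of treatment with bemcentinib". The same paragraph says patients should not be on gastric protectants when they start bemcentinib. The reason given is that pH studies suggest the drug is more soluble in acid.
- SAP 4.4: the investigator may start them "in the evening for symptomatic relief following one week's treatment with bemcentinib".

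**Washout before bemcentinib.**
- Protocol 10.2, exclusion 13 (the synopsis has the same rule): "proton pump inhibitors or antacids within 3 days or 5 half-lives of administration of bemcentinib, whichever is longer".
- Protocol 12.3: patients on "inhibitors or proton pump inhibitors within 3 days of administration of bemcentinib will be excluded". SAP 4.4 also gives 3 days.
- Protocol 7.2.3.1 gives no washout length.

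**Drug classes.** Exclusion 13 and 7.2.3.1 name H2 blockers, proton pump inhibitors and antacids as three groups. In 12.3 and SAP 4.4 the word antacid stands directly before histamine receptor 2 inhibitors, so it is unclear whether plain antacids are covered.

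**The concern.** Two sites could manage the first week differently and each comply with the section it followed. The week in question contains the loading doses, which are the first three doses of Cycle 1, and the dense PK and ECG sampling on Days 1 to 4. Demand for these drugs is plausible then, because Protocol 7.2.3 reports that gastrointestinal toxicity is more pronounced during and shortly after loading.

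At stake is how clean the early PK data are, together with the planned modelling of QTcF against plasma concentration (Protocol 16.4.2). Between-subject variability in exposure was already high in the healthy-volunteer study, and Protocol 7.2.2 attributes it most probably to absorption. A drug that may alter absorption, used in some patients and not others, would add to that variability unless it is identified.

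**Working it through.** The plan states no figure to reproduce here. The check is a comparison of the passages plus three small counts.

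**1. Timing.** Protocol 12.3 has no waiting period; Protocol 7.2.3.1 has at least one week and SAP 4.4 one week. The loading doses are on Days 1, 2 and 3. Days 1 to 7 are therefore open under 12.3 and closed under the other two. The conflict exists within the protocol itself (7.2.3.1 against 12.3) and does not depend on the SAP.

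**2. Washout.** The rules are 3 days = 72 h (12.3, SAP 4.4) and the longer of 72 h and 5 × half-life (exclusion 13). They differ only when

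5 × half-life > 72 h, that is, half-life > 72 / 5 = 14.4 h.

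Below 14.4 h they coincide. The documents give no half-life for any acid-reducing drug.

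**3. PK samples that could be affected.** Protocol Table 11 gives these Day 1 to 4 samples:

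| Day | Samples | Number |
|---|---|---|
| 1 | pre-dose, 2, 4, 6 h | 4 |
| 2 | 24, 30 h | 2 |
| 3 | 48 h, then 2, 4, 6, 8 h after the Day 3 dose | 5 |
| 4 | pre-dose | 1 |
| Total | | 12 |

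Assume bemcentinib is taken in the morning and the acid reducer is first taken on the evening of Day 1, the earliest use 12.3 allows under evening-only dosing. The four Day 1 samples then come before it. That leaves 2 + 5 + 1 = 8 of 12. This is an upper limit. The 24 h sample precedes the second bemcentinib dose, so it could change only if the first dose were still being absorbed that evening. That is possible: Protocol 7.2.2 reports mean peak concentrations at 8 to 23 h in fasted healthy volunteers.

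**4. ECG time-points.** The footnotes to Protocol Tables 4 to 6 give 4 on Day 1 (pre-dose, 2, 4, 6 h), 2 on Day 2, 1 on Day 3 and 4 on Day 4, which is 11 in all. From Day 2 onward there are 2 + 1 + 4 = 7.

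**5. Size of the effect.** Protocol 7.2.3.1 gives a direction for solubility and no effect on exposure. The change in AUC or Cmax cannot be computed from the documents.

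**The case against.** Much of the opposing case is sound.

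- **The shared evening rule already limits any interaction.** Bemcentinib is normally taken fasted on waking, so evening use separates the two drugs. This stands. It is also why a reader should not infer that all 12 intensive PK samples are exposed: the four Day 1 samples precede any use that 12.3 permits.
- **The washout texts can be applied together.** A patient treated within 3 days is excluded under both, and exclusion 13 adds a longer period for some agents. This largely stands. The difference is narrow, and SAP 4.4 sides with 12.3 on it.
- **The SAP is weak evidence against this protocol.** SAP section 1 covers four country protocols and lists US version 9.0, while the protocol reviewed is US version 10.0. This is fair, but 7.2.3.1 and 12.3 conflict inside the same document.
- **The PK methods are in a separate plan that is not available here.** This stands. A reader might infer that acid-reducer use goes unexamined in the PK analysis, and the documents do not support that. Protocol 12.3 requires every medication to be recorded in the eCRF, and SAP Listing 16.2.4.6 will list them.
- **Little enrolment may remain.** Protocol 16.8 reports Parts A and B3 complete and B2 enrolment complete, with B1, B4 and B5 enrolling as of 17 March 2020. A clarified text helps only new patients. Flagging existing data does not depend on enrolment.

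None of this restores the one-week condition to 12.3.

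**Conclusion.** The inconsistency is real and minor. Protocol 12.3 omits the one-week condition found in Protocol 7.2.3.1 and SAP 4.4. Exclusion 13 differs from 12.3 and SAP 4.4 on washout, for half-lives above 14.4 h only, and on whether antacids are named.

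The reach is at most 8 of 12 PK samples and 7 of 11 ECG time-points on Days 1 to 4, in any patient given such a drug in that window. These counts assume morning dosing and a first evening dose on Day 1. If bemcentinib is taken later in the day, as the light-meal option permits, the separation is smaller and the counts could differ.

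A reader might go further and conclude that loading-phase exposure is in fact lowered. The documents do not show that. They report a solubility finding without an effect on exposure, and do not say how many patients took these drugs in Week 1. The safety endpoints remain defined as they are, and the objective response test is not directly affected.

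**What to change.** Reconcile Protocol 12.3, Protocol 7.2.3.1, exclusion criterion 13 (with its synopsis copy) and SAP 4.4 to one timing rule, one washout rule and one list of drug classes. Which rule applies is a clinical decision for the sponsor.

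In the separate PK analysis plan, if it is not already there, flag every patient with any acid-reducing drug in Days 1 to 7, using the eCRF concomitant medication data. Present the PK results with and without those patients, and include Part A, where the data already exist.

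The cost is a text clarification in the protocol and SAP, plus one derived flag and a repeat of the PK summaries. No new data collection is needed.
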